6.8. Withdrawal of participants from treatment or assessment

Participants will be withdrawn from the trial if they; discontinue the trial medication for >7 days; cease effective contraception, become pregnant or withdraw consent.

Discontinuation due to adverse events (both serious and non-serious) may be a criterion for withdrawal, but is not mandatory, and could be either at the request of the participant or the discretion of the investigator. Withdrawal of consent will not require any data to be destroyed. This instead is termed 'revocation of consent' and has an associated form to be completed.

6.9. Treatments

1000 mg/day of Garcinia mangostana Linn will be used in the study. Placebo capsules matched in appearance and taste will be used.

6.10. Doses and treatment regimens

Trial medication will be dispensed on a monthly basis, so there will be a total of six dispensations per participant. The medication will be provided to the participant after the baseline visit has been completed and the participant has been randomised. The trial medications will be supplied by the site pharmacy. Participants will be instructed to return all containers to allow capsule counts by the trial monitor and the trial pharmacist. In the event that face-to-face visits are unable to be conducted due to safety concerns, medications will either be delivered to participants front doors or mailed directly to participants. Participants will be provided with reply paid envelopes to post remaining medication back to the researcher.

6.10.1. Labelling

The labelling of study medication will comply with local regulatory GCP requirements.

6.10.2. Storage

All investigational products will be kept in a secure location under appropriate storage conditions. A description of the appropriate storage should be specified on the investigational product label.

6.10.3. Accountability

Concordant with SPIRIT guidelines, adherence will be assessed by pill counts of returned medication packs. Adverse effects are recorded and monitored and will be reviewed by our independent DSMB.

6.11. Blinding and unblinding the study

6.11.1. Methods for ensuring blinding

Blindness will be maintained by ensuring that the packaging, appearance, colour and taste of mangosteen pericarp and placebo capsules are identical. Blindness will also be maintained by the use of an anonymous Participant-ID and not allowing study personnel access to the randomisation code unless in an emergency. The research assistants will remain blinded throughout the entire trial. Analysis of the data will also be conducted blind to the statistician and Investigators.

6.11.2. Methods for unblinding the study

Protocol: MANGO BD

Individual treatment codes, indicating the treatment randomisation for each randomised participant, will be available to the pharmacists at the participating sites. The treatment code must not be broken throughout the study period except in medical emergencies when the appropriate management of the participant necessitates knowledge of the treatment randomisation. All cases of emergency unblinding must be thoroughly documented and require reporting to the DSMB (if that had not occurred previously). Participants will be notified at the completion of all participants in the study, which arm of the study they took part in.

6.12. Prohibited concomitant treatment(s)

Prohibited medication prior to the study: 6.12.1.

Any preparation of mangosteen pericarp will be prohibited prior to study entry.

6.12.2. Prohibited medication during the study:

Any preparation of mangosteen pericarp will be prohibited during the trial.

6.13. Safety measures and variables

The definitions of adverse events (AEs) and serious adverse events (SAEs) are given below.

6.13.1. Adverse event

An adverse event is the development of an undesirable medical condition or the deterioration of a pre-existing medical condition following or during exposure to a pharmaceutical product, whether or not considered causally related to the product. An undesirable medical condition can be symptoms (e.g., nausea, chest pain), signs (e.g., tachycardia, enlarged liver) or the abnormal results of an investigation (e.g., laboratory findings, electrocardiogram). In clinical studies, an AE can include an undesirable medical condition occurring at any time, including washout periods, even if no study treatment has been administered.

6.13.2. Serious adverse event

A serious adverse event is an AE occurring during the treatment phase (i.e. baseline to week 24), of the investigational product, comparator or placebo, which fulfils one or more of the following criteria:

- results in death
- is immediately life-threatening
- requires in-patient hospitalisation or prolongation of existing hospitalisation
- results in persistent or significant disability or incapacity
- is a congenital abnormality or birth defect
- is an important medical event that may jeopardise the patient or may require medical intervention to prevent one of the outcomes listed above.

Protocol: MANGO BD

The causality of SAEs (i.e., their relationship to study treatment) will be assessed by the investigator(s). Note that SAEs that could be associated with any study procedure should also be reported. For such events the casual relationship is implied as "yes".

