3.1.1. Aims

The primary aim of this study is to investigate the efficacy of adjunctive mangosteen pericarp 1000mg/day for the treatment of bipolar depression using a 24-Week randomised, placebo-controlled trial. The primary outcome measure will be the change in severity of mood symptoms, measured using the Montgomery Åsberg Depression Rating Scale (MADRS). Secondary outcomes include global psychopathology, substance use, functioning, quality of life, and safety and tolerability data. A follow-up interview will be conducted 4 weeks post-treatment to determine any outcomes following cessation of the trial agent.

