4.9. Exploration of biological correlates

Blood samples will be obtained at baseline and week 24, to be stored and later analysed for biological correlates based on preclinical evidence including markers of antioxidant defence (including antioxidant levels), oxidative stress (including markers of lipid peroxidation and protein carbonylation), and markers of inflammation (including IL1, IL6, CRP and $TNF\alpha$), which interact with oxidative stress.

Table 1: Instruments / procedures to be implemented at each study visit:

| VISIT | 1 | 2 | 3 | 4 | 5 | 6 | 7 | 8 |
|---------------------------------|-----------|------------|------------|------------|------------|------------|---------|-----------------|
| | Baseline/ | Interim | Interim | Interim | Interim | Interim | Primary | Post- |
| | Screening | assessment | assessment | assessment | assessment | assessment | End- | discontinuation |
| | * | | | | | | point | follow-up |
| WEEK | 0 | 4 | 8 | 12 | 16 | 20 | 24 | 28 |
| SCREENING AND CONSENT | | | | | | | | |
| Informed consent | Х | | | | | | | |
| Inclusion/exclusion criteria | X | | | | | | | |
| Demographics | X | | | | | | | |
| Medical history | X | | | | | | | |
| Psychiatric and family history | X | | | | | | | |
| Concomitant medication | X | Χ | Χ | X | X | X | Х | X |
| Pregnancy test (females only)** | X | | | | | | | |
| SCID-5-RV | X | | | | | | | |
| SAFETY | | | | | | | | |
| Adverse Events | X | Χ | Χ | X | X | X | Χ | X |
| EFFICIACY | | | | | | | | |
| MADRS | X | X | Χ | X | X | X | Х | Χ |
| BDRS | Х | Χ | Χ | X | X | X | Χ | Χ |
| YMRS | Х | Χ | Χ | X | X | X | Χ | Χ |
| HAM-A | X | Χ | Χ | X | X | X | Х | X |
| CGI-S | X | X | X | X | X | X | Χ | Χ |
| CGI-I | | Χ | X | X | X | X | Χ | Х |
| PGI | | Χ | Χ | X | X | X | Χ | X |
| COGNITION | | | | | | | | |
| Digit span forwards | X | | | | | | Χ | |
| Digit span backwards | X | | | | | | Χ | |
| Trail making | X | | | | | | Χ | |
| Symbol digit task | X | | | | | | Х | |
| FUNCTIONING AND QUALITY OF LIFE | | | | | | | | |
| Q-LES-Q | Х | X | X | X | X | X | Χ | Χ |
| SOFAS | X | X | Χ | X | X | X | Χ | Χ |
| LIFE-RIFT | X | Χ | Χ | X | X | X | Х | Χ |
| ASSESSMENT OF PREDICTORS AND | | | | | | | | |
| MODERATORS | | | | | | | | |
| SAPAS | Х | | | | | | | |
| DQES V.2 | X | | | | | | | |
| HEALTH ECONOMICS | | | | | | | | |

| VISIT | 1 | 2 | 3 | 4 | 5 | 6 | 7 | 8 |

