6.7. Frequency of visits and follow up period

Participants will be assessed at baseline, regular 4-weekly intervals throughout the 24-week trial (weeks 4, 8, 12, 16, 20, 24), and at a post-discontinuation follow-up 4 weeks after completion of the trial as outlined in Table 1. Interviews with participants will take an average of 40-60 minutes. If participants cannot be seen face-to-face due to safety concerns, interviews will be conducted via online platforms such as Zoom, Skype or over teleconference as a last resort. Once enrolled, participants will be reimbursed for travel up to the value of \$20, per visit, or to cover internet expenses. Visits must occur within one week of the pre-determined date (based on baseline visit date). If a visit occurs more than 7 days after the pre-determined date, this will be a deviation from protocol. If participants cannot attend any visit before 2 weeks from the pre-determined date, this visit will be skipped until the next scheduled assessment. A skipped visit will also be a deviation from protocol.

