6.13.2.1. Recording of adverse events

Adverse events will be collected from the time that Informed Consent has been obtained until the end of the 24 week intervention period. At each visit, participants will be asked if they have had any health problems since the previous visit. All AEs will be recorded appropriately, whether or not considered related to the investigational product. This will include AEs spontaneously reported by the participant and/or observed by the staff as well as AEs reported in response to a direct question e.g. "Have you had any health problems since your last visit". The current study also encourages reports of unexpected improvements as part of the AE reporting.

For each AE the following parameters will be described: a description of the event, start and stop date, action taken with regards to investigational product (if applicable), outcome, if the AE caused the patient to discontinue, a statement if the AE fulfils the criteria for a SAE or not, the treating doctor or investigator's assessment of the causal relationship between the event and the investigational product, treatment for the AE and the intensity of the AE.

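### The AE and SAE windows contradict each other: the SAE definition runs only from baseline to week 24, although AEs are collected from consent and Table 1 records them at week 28

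*Protocol*

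**What the plan says.** The protocol sets the period for safety events in several places.

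- Section 6.13.2 makes timing part of the SAE definition: "A serious adverse event is an AE occurring during the treatment phase (i.e. baseline to week 24"). The usual seriousness criteria follow. It adds that SAEs linked to a study procedure should also be reported.
- Section 6.13.2.1 says: "Adverse events will be collected from the time that Informed Consent has been obtained until the end of the 24 week intervention period". It continues: "At each visit, participants will be asked if they have had any health problems since the previous visit".
- Table 1 (in section 4.9) has the visit row "WEEK | 0 | 4 | 8 | 12 | 16 | 20 | 24 | 28", and its row "Adverse Events" is marked at all eight visits, including the post-discontinuation visit at week 28.
- Section 6.13.1 lets an AE arise at any time, washout included, even when no study treatment has been given.
- Section 6.13.2.2 follows AEs after week 24 until they resolve or until 7 days after study completion or withdrawal.
- Section 7.2 follows pregnancy outcomes to week 28 and treats miscarriages and birth defects as SAEs, with no week-24 limit.

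The week-28 visit serves a stated aim (section 3.1.1): "A follow-up interview will be conducted 4 weeks post-treatment to determine any outcomes following cessation of the trial agent".

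**The concern.** Whether an event is serious is normally a matter of its outcome, and the period of collection is set separately. Section 6.13.2 merges the two, so an event that meets every seriousness criterion stops being an SAE because of its date. The period so defined is narrower than AE collection at the start (baseline, not consent) and narrower than Table 1 at the end (week 24, not week 28).

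What is at stake is the reporting route. Section 6.13.3 has staff tell the trial coordinator of an SAE at once, with reports to authorities due within 24 hours, and nothing but SAE status sets this in motion. The weeks after stopping the agent are also of interest in themselves: section 3.1.1 names safety and tolerability among the secondary outcomes, and hypothesis iii in section 3.1.3 concerns the four weeks after discontinuation. The introduction (sections 2.1 and 2.2) describes bipolar depression as carrying a high risk of suicide, so serious events in that period cannot be dismissed as remote.

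**Working it through.** No figure in the plan needs to be reproduced. The check sets the sections side by side and then follows an event through them.

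**Windows as stated**

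| Place | Subject | Start | End |
|---|---|---|---|
| 6.13.1 | what can be an AE | any time | any time |
| 6.13.2 | what can be an SAE | baseline | week 24 |
| 6.13.2.1, first sentence | AE collection | consent | week 24 |
| 6.13.2.1, visit question, with Table 1 | AE enquiry | first visit | week 28 |
| 6.13.2.2 | follow-up of AEs after week 24 | week 24 | resolution, or 7 days after completion or withdrawal |
| 7.2 | miscarriage and birth defect as SAE | no limit stated | pregnancy outcomes followed to week 28 |

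**An unplanned hospitalisation in week 26**

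1. Section 6.13.1: it is an AE.
2. Section 6.13.2.1 collects AEs only "until the end of the 24 week intervention period", so on that sentence it is not collected. On Table 1 and the visit question it is recorded at week 28. The two instructions conflict.
3. If it is recorded, section 6.13.2.1 requires the record to state whether the SAE criteria are met. Under section 6.13.2 the answer is no, because week 26 lies outside the treatment phase.
4. Section 6.13.3 is therefore not triggered.

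**The same event after consent and before baseline**

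Section 6.13.2.1 collects it as an AE, because collection starts at consent. Section 6.13.2 excludes it as an SAE, because the definition starts at baseline. The interval can be real: the footnote to Table 1 allows screening and baseline to be split, and section 4.5.1 provides for a delay of more than 7 days by repeating the MADRS. The protocol states no maximum length.

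**Can the week-28 mark mean only follow-up of ongoing AEs?**

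- Sections 5.3 and 6.7 place the last visit after completion; in 6.7 it is "at a post-discontinuation follow-up 4 weeks after completion of the trial as outlined in Table 1". Completion is then week 24, and follow-up of unresolved AEs ends at 24 + 1 = week 25, which is 28 − 25 = 3 weeks before the week-28 visit.
- If completion meant week 28, follow-up would run to week 29. The question asked at each visit would still concern new problems since week 24.

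Neither reading removes the conflict.

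**Size of the gap after treatment**

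- Scheduled weeks outside the SAE definition: 28 − 24 = 4, and 4/28 = 14.3%.
- Exposure under the planned 20% attrition (section 9.3): 150 × 0.8 = 120 participants; 120 × 4 = 480 person-weeks; 480/52 = 9.2 person-years. This assumes that all 120 are observed to week 28, which the protocol does not state.

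The protocol gives no rate of serious events, so an expected number of unclassified events cannot be derived.

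**The case against.** Several stronger readings are tempting, and the protocol does not support them.

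- *Late serious events escape the DSMB.* DSMB review is not tied to SAE status. Section 4.7 has all AEs recorded and monitored and the DSMB reviewing study reports, and section 6.10.3 sends adverse effects to it. An event recorded at week 28 can reach the DSMB as an AE. What is lost is SAE classification and the prompt route of section 6.13.3.
- *The comparison of SAEs between arms is distorted.* Only section 6.13.2 gives a general SAE window, and Table 1 has no SAE row, so SAEs would be cut off alike at every site. AE collection at week 28 could differ between sites, but allocation is blinded and nothing in the document points to a difference by arm.
- *Participants at risk of suicide are unprotected after week 24.* The steps in section 6.15 carry no week-24 limit and do not depend on SAE status, and the MADRS, whose suicide item prompts them, is scheduled at week 28. The gap is in reporting.
- *14% of serious events are missed.* The figure is a share of scheduled time only.

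Two further points have some force. Screening and baseline share one column in Table 1, so the interval before baseline may often be short, and the sentence on procedure-related SAEs can be read as bringing in such events. On that reading, a serious event before baseline that is unrelated to a procedure still falls outside. Section 7.2 is also a true exception, though confined to pregnancy outcomes; it shows that the week-24 limit is not applied consistently.

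**Conclusion.** The contradiction stands and rests on the current text alone. Outside the pregnancy exception, a serious event in weeks 24 to 28, or between consent and baseline, is not an SAE as defined and does not set off the section 6.13.3 route. The affected time after treatment is 4 of 28 scheduled weeks (14.3%), about 480 person-weeks if planned retention holds to week 28. The time before baseline is not fixed by the protocol.

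The conclusion assumes that sites apply section 6.13.2 as worded; a site that reported on seriousness alone would be departing from it. For a participant who stops treatment before week 24 the definition is ambiguous, because the treatment phase is equated with baseline to week 24 whether or not that person is still taking capsules. The primary efficacy analysis is not affected. The point should be corrected because a stated safety rule gives the wrong classification and the repair is cheap.

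**What to change.** Reconcile Table 1 with sections 6.13.1, 6.13.2, 6.13.2.1, 6.13.2.2 and 7.2 so that they share one stated AE/SAE window, starting at informed consent and covering the week-28 visit already scheduled. Remove the time limit from the SAE definition, so that seriousness depends on the listed criteria and the collection period is stated once, elsewhere. Make clear what completion means in section 6.13.2.2, and how the window applies to those who leave early. Tabulate on-treatment and post-discontinuation events separately by arm, so that the wider window does not blur the on-treatment comparison.

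The cost is protocol wording and probably a few more SAE reports. The week-28 visit and its question about health problems already exist. The point does not call for a fixed period of collection after the last dose: the protocol has none, and it would mean new contacts with withdrawn participants, for whom section 6.13.2.2 provides only AE follow-up and one call.

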6.13.2.1. Recording of adverse events

Adverse events will be collected from the time that Informed Consent has been obtained until the end of the 24 week intervention period. At each visit, participants will be asked if they have had any health problems since the previous visit. All AEs will be recorded appropriately, whether or not considered related to the investigational product. This will include AEs spontaneously reported by the participant and/or observed by the staff as well as AEs reported in response to a direct question e.g. "Have you had any health problems since your last visit". The current study also encourages reports of unexpected improvements as part of the AE reporting.

For each AE the following parameters will be described: a description of the event, start and stop date, action taken with regards to investigational product (if applicable), outcome, if the AE caused the patient to discontinue, a statement if the AE fulfils the criteria for a SAE or not, the treating doctor or investigator's assessment of the causal relationship between the event and the investigational product, treatment for the AE and the intensity of the AE.

6.13.2.2. Follow-up of adverse events

After the 24 week intervention period, adverse events will be followed up until either of the following conditions is met:

- The adverse event is resolved; or
- 7 days following the completion of the study or study withdrawal. Participants should be called at this time and told that they should contact their own treating physician if adverse events persist. Further follow-up of an adverse event can occur at the discretion of the treating physician or Investigator.

6.13.3. Reporting of serious adverse events

Reporting of SAEs to regulatory authorities will be done by the investigator (or delegate) in accordance with local regulations. SAEs will also be reported to the relevant HRECs according to policy and guidelines. The project manager and coordinating investigator or their nominated delegates will be responsible for reporting the SAEs to the appropriate authorities. If unblinding is required, a report will also be sent to the Therapeutic Goods Administration, or relevant regulatory body. **Trial staff must report SAE's to the trial coordinator immediately as they are required to be reported to the appropriate regulatory agencies within 24 hours.**

6.14. Other safety measurements and variables

If the participant is female, of child-bearing potential and sexually active, urine pregnancy tests will be conducted at baseline.

6.15. Managing suicidality

All participants will be required to nominate a current treating physician on enrollment into the study and will be notified that that physician may be contacted, should the research team feel it is appropriate. Should a participant express suicidal ideation with a specific plan or intent (a MADRS suicide item score of 5 or 6), the researcher will strongly advise the participant to inform their current treating physician, and will also attempt to contact the treating physician directly. Should the researcher have significant concerns for the immediate safety of the participant (e.g. severe suicidality with immediate risk or a recent, unreported suicide attempt) the researcher will seek advice from the PI, and will take appropriate steps to ensure participant safety (including informing the treating physician and assisting the person to appropriate care, for example by taking the person to the emergency department or calling an ambulance).

7. Procedures in case of emergency or pregnancy

7.1. Procedures in case of medical emergency

The chief investigator (or their delegate) is responsible for ensuring that procedures and expertise are available to handle medical emergencies during the study. A medical emergency usually constitutes an SAE and should be reported.

7.2. Procedures in case of pregnancy

In case of pregnancy, treatment with study drug should immediately be terminated. Pregnancy itself is not regarded as a serious adverse event unless there is a suspicion that the investigational product under study may have interfered with the effectiveness of a contraceptive medication. However, the outcome of all pregnancies (spontaneous miscarriage, elective termination, normal birth or congenital abnormality) will be followed up until week 28 and documented. All reports of congenital abnormalities/birth defects are SAEs. Spontaneous miscarriages will also be reported and handled as SAEs. Elective abortions without complications will not be handled as AEs.

8. Data Management

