4.5.2. Exclusion Criteria

- Participants with a known or suspected active systemic medical disorder,
- Individuals who are pregnant or lactating (participants will be requested to conduct a urine pregnancy test if sexually active and of child-bearing age),
- Participants currently enrolled in any other intervention study will be excluded,
- Individuals who are intolerant, allergic to or have had an anaphylactic reaction to any components of the preparation,
- Inability to comply with either the requirements of informed consent or the treatment protocol.

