5.3. Study Design

This is a 24-week, double blind, randomised, placebo-controlled trial of adjunctive *Garcinia mangostana* Linn in the treatment of bipolar depression (n=150). The duration of the current trial will be 24 weeks concordant with our pilot data. A follow-up interview will be scheduled 4 weeks after completion of the study. The trial will be conducted following approval from the relevant ethics committees, and conducted in accordance with the Good Clinical Practice guidelines. The trial will be conducted according to Australian Clinical Trial guidelines and the National Ethical guidelines for Human Research. This protocol was developed in accordance with Standard Protocol Items Recommendations for Intervention Trials (SPIRIT) 2013 guidelines, and findings will be reported using CONSORT guidelines. All participants will give informed consent prior to enrolment. Participants will be withdrawn from the study if they withdraw consent or at the discretion of the investigators.

6. Procedure

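### Pregnancy follow-up stops at week 28, before any term birth after on-trial conception, and sections 7.2 and 6.13.2 disagree on which pregnancy outcomes are SAEs

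*Protocol*

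**What the plan says.** Section 7.2 of the protocol (Procedures in case of pregnancy) states that "the outcome of all pregnancies (spontaneous miscarriage, elective termination, normal birth or congenital abnormality) will be followed up until week 28 and documented". It adds, with no time limit, that "All reports of congenital abnormalities/birth defects are SAEs", and it handles spontaneous miscarriages as SAEs too.

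Section 6.13.2 (Serious adverse event) sets a window: "A serious adverse event is an AE occurring during the treatment phase (i.e. baseline to week 24". Congenital abnormality or birth defect is one of the criteria listed under that definition.

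The calendar comes from section 5.3: "The duration of the current trial will be 24 weeks concordant with our pilot data", and "A follow-up interview will be scheduled 4 weeks after completion of the study". Table 1 accordingly places the post-discontinuation visit at week 28. Section 4.5.2 excludes "Individuals who are pregnant or lactating", and sections 4.6 and 6.8 withdraw participants who become pregnant.

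**The concern.** Two of the four outcomes that section 7.2 undertakes to document, normal birth and congenital abnormality, are wholly or largely settled at delivery. The cut-off is the trial's last visit, and nothing in the rule ties it to the course of the pregnancy. If staff follow the sentence exactly, a pregnancy still continuing at week 28 is closed with its outcome not known, although learning the outcome is the purpose of the provision.

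The SAE definition adds a second difficulty. Section 6.13.3 requires staff to report SAEs immediately because regulatory reporting is due within 24 hours. For a miscarriage or a birth defect that comes to light after week 24, the protocol gives two answers on whether it is an SAE.

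What is at stake is the completeness of the safety data on exposed pregnancies and consistent SAE reporting. The primary endpoint, the randomisation and the efficacy analysis are not touched.

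**Working it through.** **Inputs from the protocol**
- Treatment lasts 24 weeks and the follow-up interview comes 4 weeks later (section 5.3).
- Pregnancy is excluded at entry (section 4.5.2), so an on-trial conception falls at week *c* with *c* ≥ 0.
- Pregnancy outcomes are followed to week 28 (section 7.2).
- SAEs are limited to baseline to week 24 (section 6.13.2).

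**Assumptions, not in the protocol**
- Gestational age is counted from the last menstrual period, about 2 weeks before conception.
- Term is 37 to 40 gestational weeks, that is, 35 to 38 weeks after conception.

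**Step 1: the plan's own figure.** 24 + 4 = 28, so week 28 is the last visit.

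**Step 2: how far a pregnancy has progressed at the cut-off.** Gestational age at trial week 28 = (28 − *c*) + 2. The shortfall is 37 or 40 minus that value. Term falls at trial week *c* + 35 to *c* + 38.

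| Conception (trial week) | Gestational weeks at trial week 28 | Short of 37 / 40 weeks | Trial weeks at which term falls |
|---|---|---|---|
| 0 | 30 | 7 / 10 | 35–38 |
| 4 | 26 | 11 / 14 | 39–42 |
| 8 | 22 | 15 / 18 | 43–46 |
| 12 | 18 | 19 / 22 | 47–50 |
| 16 | 14 | 23 / 26 | 51–54 |
| 20 | 10 | 27 / 30 | 55–58 |
| 24 | 6 | 31 / 34 | 59–62 |

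Even the earliest on-trial conception is at least 7 weeks from term when follow-up ends.

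**Step 3: could a pregnancy missed at entry reach term?** It would have to satisfy 28 + *x* + 2 = 37, where *x* is the number of weeks from conception to baseline. This gives *x* = 7. The footnote to Table 1 does not make the baseline test compulsory in every case, so a missed pregnancy is conceivable, but it would breach the exclusion criterion.

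**Step 4: the other reading of week 28.** Taken as gestational week 28, the cut-off is still 37 − 28 = 9 to 40 − 28 = 12 weeks before term. The conclusion does not depend on the reading.

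**Step 5: the SAE window.** At trial week 24 a week-0 conception has reached (24 − 0) + 2 = 26 gestational weeks. Under section 6.13.2 a birth defect therefore counts only if it is recognised by that point or earlier in the pregnancy. Take a miscarriage at trial week 26: section 7.2 makes it an SAE, while section 6.13.2 places it outside the window.

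**Step 6: is there a provision elsewhere?** Section 6.13.2.1 collects adverse events to the end of the 24-week intervention. Section 6.13.2.2 follows them until they resolve or until 7 days after study completion or withdrawal, with anything further left to discretion. No section extends the follow-up of a pregnancy itself beyond week 28.

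**The case against.** A reader might infer that the birth and congenital-abnormality outcomes cannot be observed at all. The protocol does not support that. An abnormality can be found before birth, after a pregnancy loss or at a preterm delivery, and conceptions at weeks 0, 4 and 8 have reached 30, 26 and 22 gestational weeks by the cut-off. Miscarriage and termination can also fall inside the window, although a conception near week 24 has only about 4 weeks of follow-up. A pregnancy that ends in either way before week 28 closes with a known outcome.

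A reader might also infer that a birth defect could never be an SAE under section 6.13.2. That goes too far as well. One recognised by week 24 meets both the criterion and the window, and section 7.2 makes every such report an SAE whatever its date. One may argue that the specific rule in 7.2 governs over the general definition. The protocol does not say so, and the conflict after week 24 remains.

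Section 6.13.2.2 gives partial relief, because an event already recorded as an adverse event may be followed further at discretion. It does not help with an uncomplicated continuing pregnancy: section 7.2 does not regard pregnancy itself as an SAE unless interference with a contraceptive is suspected.

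Finally, few pregnancies are to be expected. Effective contraception is an inclusion requirement, and participants who become pregnant or cease contraception are withdrawn. The largest shortfall, 31 to 34 weeks, belongs to conceptions at the very end of treatment, when exposure is least. These points limit the weight of the finding. They leave the contradiction between the outcome list and the cut-off in place.

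**Conclusion.** The point holds in a limited form. As written, section 7.2 cannot record a term birth after an on-trial conception, nor an abnormality that becomes apparent only at a term birth. The shortfall runs from 7–10 weeks (conception at week 0) to 31–34 weeks (conception at week 24), assuming term at 37 to 40 gestational weeks. The other listed outcomes, and abnormalities detected before birth, are captured in part.

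Secondarily, sections 7.2 and 6.13.2 classify pregnancy outcomes after week 24 differently, and nothing in the protocol says which section prevails.

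These are weeks of missing follow-up. The protocol gives no basis for an expected number of pregnancies, so the number of outcomes lost cannot be estimated, though it should be small. The matter is worth correcting because a stated rule fails its stated purpose. It is a defect of safety documentation and has no bearing on the efficacy results.

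**What to change.** 1. In section 7.2, reconcile the outcome list with the cut-off: replace the fixed week with documentation of each on-trial pregnancy until one of the listed outcomes is known. Narrowing the list to what can be seen by week 28 would also make the sentence consistent, but it would give up the birth outcomes that the provision sets out to record.
2. Reconcile section 6.13.2 with section 7.2, so that pregnancy outcomes are not subject to the week-24 limit on SAEs. Add a cross-reference between the two sections.

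The change concerns data collection and reporting only. It costs protocol wording and occasional contact after the trial for the few pregnancies expected. For a conception at week 24, contact would run to about trial week 59 to 62, that is, 31 to 34 weeks beyond the last visit (59 − 28 = 31; 62 − 28 = 34). The analysis and the trial timetable for efficacy need no change.
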